### **7.1.2 Non-Date Values**

Every effort will be made to obtain required data at each scheduled evaluation from all subjects who have been enrolled. There will be no imputation for missing data.

## **7.2 Visit Windows**

The screening assessments and the treatment/post-treatment assessments will be partitioned into the following two visit windows:

- A screening window, beginning on Day -28 and ending on Day -1.
- A treatment window, beginning on Day 1 of Cycle 1 and ending on the Study Day (see [Section 7.3](#)) corresponding with the End of Treatment visit.

Subject visits for all parts of the study (i.e., Part A, and Part B) will be presented according to the nominal visit as obtained upon the CRF. All values will be included in the subject data listings.

## **7.3 Data Derivations**

Day 1 will be the date corresponding to the first administration of study drug.

Baseline values will be considered as the last non-missing assessment prior to the first administration of study drug (ASN002). Pre-dose assessments of ECG, vital signs, and the samples for pharmacokinetics (PK) and pharmacodynamics (PD) on Day 1 of Cycle 1 will be considered the baseline assessment for

each of these respective study procedures. Assessments performed on Day 1 of Cycle 1 for all other study procedures will be assumed to have been performed prior to administration of ASN002. Unless otherwise specified, change from baseline calculations for a treatment window assessment will be the applicable treatment window assessment minus the baseline assessment.

For a given date within the treatment window, Study Day will be computed as the given date minus Day 1 of Cycle 1 plus 1 day (i.e., Study Day = Date – Day 1 of Cycle 1 + 1). For a given date within the screening window, Study Day will be computed as the given date minus Day 1 of Cycle 1 (i.e., Study Day = Date – Day 1 of Cycle 1).

For a given entry upon the Drug Log Form of the eCRF, total dose of ASN002 administered for the entry will be calculated as:

Total dose of ASN002 for entry (mg) = Total Daily Dose (mg/day) \* (Stop Date – Start Date + 1).

Furthermore, for a given date which lies between (non-inclusive) the Start Date and Stop Date, partial total dose of ASN002 for the entry can be calculated by substituting the given date for either the Stop Date or Start Date within the above formula.

For each visit over the treatment window and overall, total dose of ASN002 will be calculated as the cumulative sum of the total dose and partial total dose of ASN002 administered over the entries to the Drug Log Form pertaining to the visit (or, overall). An entry to the Drug Log Form will pertain to a given visit, if: (1) the Start Date of the entry is earlier than the date corresponding to the visit; and, (2) the Stop Date of the entry falls after the date corresponding to the immediately preceding visit.

Expected total dose of ASN002 to be administered – for, a Drug Log Form entry, a visit, or overall – will be calculated similarly, with the daily dose corresponding to the assigned treatment cohort substituted in lieu of Total Daily Dose within the above formula.

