**Part B**

During Part B of the study, dose interruption (of up to 7 days) and modification for an AE meeting the criteria for DLT is allowed. For a drug-related toxicity, the dose should be immediately interrupted and supportive care provided until the AE resolves to  $\leq$  Grade 1. After the AE resolves to  $\leq$  Grade 1, retreatment at a lower dose may be considered upon agreement between the investigator and Sponsor medical monitor. If the toxicity recurs after re-challenge at a lower dose, study treatment should be discontinued. In the absence of  $>$  Grade 1 drug-related toxicity after at least 4 weeks of study treatment, subjects may be considered for intra-patient escalation to a higher dose that has been declared safe, in agreement with the investigators and Sponsor. The decision on possible escalation to a higher dose will be made on a case by case basis.

Guidelines for dose modification for patients starting at 75 mg BID are listed in **Table 7**.

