## **10.7 Treatment Compliance**

Study drug compliance will be calculated weekly during Cycle 1. In subsequent cycles, compliance will be calculated on Day 1 prior to receiving additional ASN002. Subjects taking too much or too little study drug should be re-educated on the proper use of study drug. Repeated non-compliance (less than 80% or greater than 100%) should be evaluated by the investigator for the need to withdraw the subject.

Compliance can be assessed using the following formula:

(Number of tablets taken/number of tablets required per protocol) \* 100 = % compliance

Accidental or intentional overdoses should be reported to the sponsor/designee promptly (refer to Section 12.6.1).

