### **8.3 Protocol Deviations**

Major protocol deviations are defined to be those deviations that could potentially bias either efficacy or safety summaries of the study. Subjects associated with major protocol deviations will be identified prior to database lock.

Major deviations from the clinical protocol may include, but are not limited to:

- Subjects that were administered at least one dose of ASN002 and who did not satisfy the inclusion/exclusion criteria.
- Subjects meeting conditions for withdrawal that were not withdrawn.
- Subjects that received a prohibited concomitant medication.
- Repeated non-compliance in administration of study drug, as monitored by the study site at the assessment timepoints shown within Table 1 of Section 3.2, where non-compliance is less than 80% or greater than 105% of expected administration of study drug.

The number and percentage of subjects with major deviations and the number of deviations will be summarized by type of violation and overall. Summaries will be provided by treatment cohort and overall. The denominators for calculating percentages will be based on the number of subjects in the analysis population for each treatment cohort and overall.

Major protocol deviations will be provided in a data listing by subject.

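### SAP 7.3 fixes expected dose at the assigned-cohort dose, so a sustained dose change that the protocol permits can score as non-compliance and put the subject's place in the PP population at risk

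*SAP*

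**What the plan says.** **Expected dose.** SAP 7.3 gives administered dose for a drug-log entry as total daily dose times (stop date minus start date plus 1). Expected dose, for an entry, a visit or overall, is calculated similarly, "with the daily dose corresponding to the assigned treatment cohort substituted in lieu of Total Daily Dose within the above formula". No other SAP section defines an expected dose.

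**Permitted changes.** In Part B, protocol 8.3.3 allows interruption of up to 7 days. After resolution of the event, "retreatment at a lower dose may be considered upon agreement between the investigator and Sponsor medical monitor". It also allows case-by-case escalation after at least 4 weeks without drug-related toxicity above Grade 1. Table 7 lists 50, 75 and 100 mg BID. In Part A, the same section allows resumption at a lower dose after Cycle 1, and escalation to the MTD at the end of Part A.

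**Use of the figure.** SAP 8.3 lists, among deviations that may be major, repeated non-compliance as monitored by the site at the Table 1 timepoints, "where non-compliance is less than 80% or greater than 105% of expected administration of study drug". SAP 5.3 removes subjects with major deviations from PP and makes PP the primary efficacy population. Protocol 10.7 has sites divide tablets taken by tablets required per protocol, and sets the upper limit at 100%.

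**Partial entries.** SAP 7.3 splits a log entry at a visit only if the visit falls strictly inside it. In that case, "partial total dose of ASN002 for the entry can be calculated by substituting the given date for either the Stop Date or Start Date".

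**The concern.** The denominator does not follow the prescription. A subject who takes every prescribed tablet after a permitted reduction or escalation is still measured against the starting dose, and can fall outside the limits while following the protocol.

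If that leads to exclusion from PP, subjects leave the primary efficacy analysis because of events after treatment began. Reductions follow toxicity. Escalations require its absence for at least 4 weeks. Both may be related to exposure and response. With 14 subjects per disease cohort, one exclusion can decide the binomial test in SAP 9.1.1. The study is open-label, so a case-by-case decision about inclusion would be taken with responses known.

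**Working it through.** The documents give no worked compliance figure to reproduce, so the SAP formulas were applied directly.

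**Inputs.** Part B starting dose 75 mg BID = 150 mg/day (protocol 8.3.2). Table 7 levels 50 and 100 mg BID = 100 and 200 mg/day. Limits below 80% and above 105% (SAP 8.3). Cycle of 28 days. The 150 mg/day denominator for Part B is itself an assumption, because the SAP's definition of treatment cohort lists nine Part A cohorts and none for Part B.

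**Full cycle, full adherence to the changed dose.**
- 50 mg BID: 100/150 = 66.7%, below 80%.
- 100 mg BID: 200/150 = 133.3%, above 105%.

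**Change part-way through a cycle.** With d days at the new daily dose b, the ratio is [150 × (28 − d) + b × d] / (150 × 28).

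| New dose | d | Ratio | Flagged |
|---|---|---|---|
| 50 mg BID | 16 | 3,400/4,200 = 81.0% | no |
| 50 mg BID | 17 | 3,350/4,200 = 79.8% | yes |
| 100 mg BID | 4 | 4,400/4,200 = 104.8% | no |
| 100 mg BID | 5 | 4,450/4,200 = 106.0% | yes |

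The first assessment after a change may therefore pass. Each later full cycle at the changed dose does not.

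**Part A, one level down (protocol Table 6).** 20 to 10 mg BID = 50%. 30 to 20 and 75 to 50 mg BID, and 120 to 80 mg QD = 66.7%. 40 to 30 and 100 to 75 mg BID = 75%. All are flagged. 50 to 40 mg BID and 150 to 120 mg QD give exactly 80.0% and pass.

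**Interruption.** A 7-day interruption in 28 days scores 21/28 = 75% if entered as 0 mg (6 days 78.6%, 5 days 82.1%). It scores 100% if the days are a gap between entries, because expected dose covers only the entry's own dates. The SAP does not say which convention applies.

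**What one exclusion can do (illustration).** Against a 5% null, 3 responders in 14 gives an exact one-sided p of 0.030, which rejects at 0.05. If one dose-modified responder is removed, 2 in 13 gives 1 − 0.95^13 − 13 × 0.05 × 0.95^12 = 0.135, which does not.

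**Visit day, a minor point.** Take one continuous 150 mg/day entry over Days 1–84 with visits on Days 8, 15, 22, 29, 57 and 85. The partial-dose rule gives 8 + 8 + 8 + 8 + 29 + 28 = 89 days, or 13,350 mg. The overall total is 84 × 150 = 12,600 mg. Five interior visit days are counted twice: 750/12,600 = +6.0% on the sum of visit totals. If entries start or stop at visits, nothing is counted twice. The extra day enters administered and expected dose alike. With a reduction to 100 mg/day from Day 41, the Day 57 ratio is 3,500/4,350 = 80.5%, against 3,400/4,200 = 81.0% without the double count.

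**The case against.** The strongest reply is that SAP 8.3 never cites 7.3. It speaks of compliance monitored by the site, and the site formula divides by tablets required per protocol, which can follow a permitted change. A fully adherent subject on a reduced dose could then score 100%. The deviation must also be repeated, the list gives possibilities, and affected subjects are identified before lock. Protocol 15.9 calls for a review of whether their inclusion is appropriate. The efficacy population (EP) is analysed as support, so a large effect of exclusions would be visible.

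Most of this stands. A reader might infer that the SAP requires exclusion of dose-modified subjects; it does not. What remains is that 8.3 is the only later SAP section that sets a percentage of an expected amount, and 7.3 is the only definition of one, calculated per visit. Protocol Section 15 gives the SAP priority where the two differ. Nothing in either document says that tablets required per protocol are re-based after a dose change, or exempts permitted changes from non-compliance. A sustained change readily meets the repeated condition, since compliance is assessed every cycle.

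Three other inferences go too far. Not every assessment after a change is flagged, as the mid-cycle figures show. Not every visit day is counted twice: only dates strictly inside a log entry are, and overall exposure is unaffected. Nor can one say that skipped days go undetected. That depends on drug-log conventions outside these documents, and site tablet counts could find them.

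The 100% and 105% limits serve different decisions (evaluation for withdrawal, and deviation class), so they need not match. But SAP Section 14 reports no changes from the protocol, so the difference should be reconciled or explained.

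**Conclusion.** The point holds as a defect in the definition of expected dose, with a conditional consequence. On the 7.3 basis, a Part B subject fully adherent to a sustained permitted change from 75 mg BID scores 67% or 133% over a full cycle and breaches the limits in SAP 8.3. This can be classed as repeated non-compliance and can lead to exclusion from PP for post-treatment reasons.

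The conclusion rests on three assumptions: that expected administration in 8.3 is the 7.3 quantity, that the Part B assigned dose is 150 mg/day, and that the pre-lock review does not rescue the subject. The first is the natural reading but is not stated. The number of subjects affected cannot be derived from the documents. The double-counted visit day is a minor programming error in per-visit milligrams and has almost no bearing on PP membership.

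The plan should be corrected before database lock.

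**What to change.** **SAP 7.3.** Define expected dose as the dose prescribed on each calendar day from first to last dose, with protocol-permitted modifications and interruptions applied, for Part B as well as Part A. State whether interruption days and missed days are recorded as 0 mg entries or as gaps. A permitted interruption should carry zero expected dose; a missed day should keep its prescribed dose in the denominator. Full adherence then scores 100% after a reduction (50/50), after an escalation (100/100) and across a 7-day interruption (21/21 days).

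**SAP 8.3.** State that changes made under protocol 8.3.3 are not non-compliance. Say which compliance calculation is used, and cite Table 2 as well as Table 1. Reconcile the upper limit with protocol 10.7, or explain the difference in Section 14.

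**Visit totals.** Use non-overlapping intervals from the preceding visit day to the day before the current visit, starting with Day 1. A weekly interval then counts 7 days and a cycle 28, and the 84-day example sums to 12,600 mg. Intervals that run from the day after one visit through the next visit day would be less suitable: they can lose Day 1 and count visit-day doses not yet taken.

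The cost is SAP wording and programming, plus confirmation of the drug-log convention. No new data collection is foreseen, provided the log or dosing records show the prescribed dose and the dates of each permitted change.

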## **8 STUDY POPULATION**

Unless otherwise stated, all study population analyses will be performed against the Safety Population.

### **8.1 Subject Enrollment**

Subject enrollment will be summarized as the number and percentage for each analysis population (EP, PP, and Safety) by treatment cohort and overall (all treatment cohorts combined). The denominators for calculating percentages will be based on the number of subjects in each analysis population by treatment cohort and overall.

Enrollment information will be provided in a data listing by subject.

### **8.2 Subject Disposition**

Subject disposition will be summarized by treatment cohort and overall. The number and percentage of subjects who are still on treatment on this study or who have rolled over to the extension study, and the number and percentage of subjects discontinued from the study will be presented by reason for discontinuation. The denominators for calculating the percentages will be based on the number of subjects in the analysis population by treatment cohort and overall.

Discontinued subjects will be provided in a data listing by subject.

### **8.3 Protocol Deviations**

Major protocol deviations are defined to be those deviations that could potentially bias either efficacy or safety summaries of the study. Subjects associated with major protocol deviations will be identified prior to database lock.

Major deviations from the clinical protocol may include, but are not limited to:

- Subjects that were administered at least one dose of ASN002 and who did not satisfy the inclusion/exclusion criteria.
- Subjects meeting conditions for withdrawal that were not withdrawn.
- Subjects that received a prohibited concomitant medication.
- Repeated non-compliance in administration of study drug, as monitored by the study site at the assessment timepoints shown within Table 1 of Section 3.2, where non-compliance is less than 80% or greater than 105% of expected administration of study drug.

The number and percentage of subjects with major deviations and the number of deviations will be summarized by type of violation and overall. Summaries will be provided by treatment cohort and overall. The denominators for calculating percentages will be based on the number of subjects in the analysis population for each treatment cohort and overall.

Major protocol deviations will be provided in a data listing by subject.

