### **9.3 Subject Discontinuation Criteria**

Study discontinuation will occur when a subject who signed informed consent ceases participation in the study. Subjects can be discontinued from the study for one of the following reasons:

- An adverse event;
- Progression of disease;
- Death;
- A protocol violation (reason must be specified, for example: lack of compliance, use of a prohibited concomitant medication, failure to meet inclusion/exclusion criteria after study entry, etc.);
- Withdrawal of consent by the subject (reason must be specified);
- The subject was “lost to follow-up”;
- Other reasons (reason must be specified, for example: the subject moved, investigator decision, sponsor decision to terminate study, etc.).

A subject is free to withdraw his consent and discontinue participation in the study at any time. The investigator must withdraw any subject from the study if the subject requests to be withdrawn. Any subject who withdraws consent as a result of an adverse event, regardless of intensity or investigator's opinion, must be reported as a discontinuation due to adverse event.

If a subject discontinues from the study, all end of treatment procedures should be conducted as detailed in **Table 1** or **Table 2**. The date a subject discontinues ASN002, and the reason for discontinuation will be recorded in the source documentation and electronic Case Report Form (eCRF). If a subject has an ongoing adverse event, the event will be followed until resolution or stabilization for at least 30 days after the last dose of ASN002. If a subject refuse to complete any of the specified End of Treatment procedures, this information will be recorded in the source documentation. A subject who discontinues from the study will not be allowed to re-enter the study.

When a subject is “lost to follow-up” (i.e., fails to return for study visits), a reasonable effort will be made to contact the subject:

1. to determine the reason for the failure to return and these contacts will be recorded in the source documents;
2. to follow up on any ongoing AEs from the previous visits;
3. to recover any unused ASN002.

The subject should be identified as “lost to follow up” in the eCRF, as appropriate.

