#### 10.6.1 Prohibited Medications

The following medications will be prohibited during the study:

- Chemotherapy, radiotherapy, immunotherapy, or investigational treatments are not allowed with concomitant use of ASN002;
- Use of localized palliative radiation for pre-existing lesions for pain control may be approved after discussion with the sponsor. The radiation field must not include any target or non-target lesions, and progressive disease must be ruled out as the underlying requirement for palliative radiotherapy.
- Therapeutic doses of anticoagulants.

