### 5.2 Efficacy Population (EP)

The efficacy population (EP) will include all subjects who have an evaluable screening and post-dose tumor assessment. The EP will be used as the supportive analysis population for summaries and analyses of the efficacy endpoints. No EP will be reflected if Part B is not completed for at least one indication.

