### 5.3 Per-Protocol (PP) Population

The PP population includes all EP subjects without major protocol deviations. The PP population will be used as the primary analysis population for efficacy summaries and analyses. No PP will be reflected if Part B is not completed for at least one indication.

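### The primary Per Protocol population may drop evaluated subjects for deviations that can follow from treatment failure, which could raise the estimated response rate

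*SAP*

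**What the plan says.** SAP 5.2 defines the starting set: "The efficacy population (EP) will include all subjects who have an evaluable screening and post-dose tumor assessment". SAP 5.3 narrows it: "The PP population includes all EP subjects without major protocol deviations". It also fixes the role: "The PP population will be used as the primary analysis population for efficacy summaries and analyses". The Efficacy Population (EP) is supportive.

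SAP 8.3 introduces its list with "Major deviations from the clinical protocol may include, but are not limited to". Two of the four examples are post-baseline events that can be tied to outcome: "Subjects meeting conditions for withdrawal that were not withdrawn" and "Subjects that received a prohibited concomitant medication". The other two are eligibility failures and repeated non-compliance with dosing. Subjects with major deviations are to be identified before database lock. Protocol 15.9 adds a pre-lock review of whether subjects with deviations belong in each analysis.

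The link to outcome comes from the protocol. Section 9.3 lists "Progression of disease" among the reasons for discontinuation, and Sections 8.1 and 8.4.2 allow treatment only while the disease has not progressed. Section 10.6.1 bars chemotherapy, radiotherapy, immunotherapy and investigational treatment during ASN002 use, together with therapeutic anticoagulation. Palliative radiation can be approved, but "progressive disease must be ruled out as the underlying requirement for palliative radiotherapy".

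**The concern.** A subject whose scan shows progression and who stays on ASN002 fits the first example. A subject who receives radiotherapy or another anticancer drug for growing disease while still taking ASN002 fits the second. Both may already have an evaluable post-dose assessment and so be in EP. SAP 9.1.1 counts no response, stable disease and progressive disease as non-response, so without the exclusion they would normally be failures in the denominator. If the deviation is classed as major, they leave the primary denominator, and any progression event leaves the PP analysis of PFS and TTP with them. Nothing in either document keeps them in PP as non-responders.

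The classification is a judgement made before lock in an open-label study, when responses can be known. Preliminary efficacy is a primary objective of Part B, and SAP 9.1.1 reports an estimated response rate for each disease cohort. What is at stake is whether that estimate describes the subjects who were treated and assessed, or a subset selected partly by how they fared.

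**Working it through.** **Inputs from the documents.** SAP 4: 14 subjects per cohort, null rate 0.05, alternative 0.40, reject at 3 or more responses, stated type I error 0.02 and power 0.9. SAP 9.1.1: one-sided binomial test, reject if p < 0.05.

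**Input not in the documents.** The shares of evaluated non-responders (q_nr) and responders (q_r) excluded for these two deviations. Both are assumptions, shown over a range.

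**Step 1: the plan's own figures.** With X binomial on 14 subjects, P(X ≥ 3) is 0.0301 at a rate of 0.05 and 0.960 at 0.40. The stated 0.02 and 0.9 do not reproduce. That is a separate matter and does not affect this point; the exact values are used below.

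**Step 2: observed rate and test when non-responders are removed.** Rate = responders / PP size. The tails are exact binomial at a rate of 0.05.

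| PP size | Rate with 3 responders | P(X ≥ 3) | P(X ≥ 2) |
|---|---|---|---|
| 14 | 21.4% | 0.0301 | 0.1530 |
| 12 | 25.0% | 0.0196 | 0.1184 |
| 10 | 30.0% | 0.0115 | 0.0861 |
| 8 | 37.5% | 0.0058 | 0.0572 |
| 7 | 42.9% | 0.0038 | 0.0444 |

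The estimate moves with each removal. The verdict does not: two responses stay above p = 0.05 down to a PP size of 8, so 3 responses are needed for sizes 8 to 14. The threshold falls to 2 only at 7 or fewer.

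**Step 3: direction.** Approximate expected PP rate = p(1 − q_r) / [p(1 − q_r) + (1 − p)(1 − q_nr)]. For example, with p = 0.20, q_nr = 0.20 and q_r = 0: 0.20 / (0.20 + 0.80 × 0.80) = 0.20 / 0.84 = 23.8%.

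| q_nr / q_r | True 5% | True 20% | True 40% |
|---|---|---|---|
| 10% / 0 | 5.5% | 21.7% | 42.6% |
| 20% / 0 | 6.2% | 23.8% | 45.5% |
| 30% / 0 | 7.0% | 26.3% | 48.8% |
| 50% / 0 | 9.5% | 33.3% | 57.1% |
| 20% / 20% | 5.0% | 20.0% | 40.0% |
| 10% / 20% | 4.5% | 18.2% | 37.2% |

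The bias is upward when q_nr exceeds q_r, zero when they are equal, and downward when responders are excluded more often.

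**Step 4: type I error of the p < 0.05 test on PP.** With a true rate of 0.05 and no responders excluded, it is 0.0301 at q_nr = 10%, 0.0305 at 20%, 0.0348 at 30% and 0.0777 at 50%. It passes 0.05 only in the last of these.

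**The case against.** A reader might infer that the SAP automatically strips treatment failures out of the primary analysis and that the response rate is therefore always inflated. The documents do not support that, for five reasons.

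- The list in SAP 8.3 is permissive, and Protocol 15.9 provides a review. Removal is automatic only once a deviation has been classed as major.
- The ordinary failure is handled properly. A subject withdrawn at progression has no such deviation and stays in PP as a non-responder.
- Protocol 10.6.1 bars other anticancer treatment only alongside ASN002, and SAP 10.3 treats medication after the last dose as post-treatment. Chemotherapy or radiotherapy begun after stopping is not a deviation.
- Responders can be excluded too: one who later progresses and stays on drug, or one given a therapeutic anticoagulant. With up to 12 months of treatment they have time to accrue a deviation.
- The plan's 10% early-termination rate cannot be borrowed as the size. It counts subjects who leave early, whereas the first route concerns subjects who stay.

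SAP 9 also uses EP for the efficacy variables, and SAP 8.3 tabulates deviations by type and lists them by subject, so a gap between PP and EP would be visible.

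All of this stands, and it narrows the point. It does not remove it. The discretion is exercised with outcomes available, and a supportive EP analysis does not correct the one named as primary.

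**Conclusion.** The point holds in a limited form. Two post-baseline events that can follow from treatment failure may be classed as major deviations, and SAP 5.3 then drops the subjects from the primary efficacy population despite an evaluable assessment. Upward bias in the response rate, and loss of progression events from PFS and TTP, require that non-responders be excluded this way more often than responders. That is the likely direction, because progression and added anticancer therapy mark failure, but it is not guaranteed.

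The size cannot be determined from the documents. The tables above are illustrations under assumed exclusion shares. The harm is mainly to the estimates. For a cohort filled to 14, the test threshold changes only if about half the cohort is removed. A cohort that closes well short of 14 would have less margin, since the threshold falls between PP sizes 8 and 7. The point lapses if Part B is not completed for at least one indication, because SAP 5.2 and 5.3 then produce neither population. It is a cheap improvement, not a threat to the trial's conclusions.

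**What to change.** In SAP 5.3 and 8.3, state that EP subjects who remain on ASN002 after a withdrawal condition, or who receive prohibited anticancer therapy or radiotherapy while on ASN002, stay in the primary efficacy analysis. Classify them by the assessments made up to the deviation: non-responders unless a complete or partial response was documented earlier. Count any documented progression as an event in PFS and TTP. Continue to report these deviations in the deviation table and listing.

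Alternatively, make EP the primary efficacy population and PP the supportive one.

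Either way, leave the eligibility and non-compliance exclusions in the PP definition as they are; this point does not bear on them.

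The cost is SAP wording only, with no new data and no change to how subjects are managed. Under the first option PP becomes slightly less strict, and under either the reported response rate may be slightly lower.
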